5.3.3 Neutropenia

To reduce the risk of severe myelosuppression events, a complete blood count (CBC) should be performed weekly during cycle 1, every 2 weeks during cycle 2, and at the start of each subsequent cycle (up to 3 days before start of new cycle) in the dose escalation phase. In the expansion phase, CBC will be performed on D1 and D8 of cycle 1, then at the start of each cycle (up to 3 days before start of new cycle). Febrile neutropenia is a life-threatening complication requiring hospitalization and urgent broad-spectrum antibiotics, as well as an aggressive search for the source and microbial cause of the episode. Growth factors to prevent neutropenia will not be administered prophylactically. If necessary, they may be administered according to accepted American Society of Clinical Oncology (ASCO) guidelines to allow re-treatment.

5.3.4 Anemia

Symptomatic anemia should be treated with red blood cell transfusion and is recommended if the hemoglobin falls below 8 g/dL. The initiation of erythropoietic therapy for the management of chemotherapy-induced anemia follows the American Society of Hematology/ASCO clinical practice guidelines (<http://www.asco.org/>).

5.3.5 Thrombocytopenia

Thrombocytopenia will be treated conservatively. In the absence of bleeding, or a necessary invasive procedure, platelet transfusions should be given for a platelet count $\leq 10,000/\text{mm}^3$. If invasive procedure(s) is (are) planned, or the patient develops bleeding, platelet transfusions should be administered in accordance with the standard of practice, usually maintaining a platelet count above $50,000/\text{mm}^3$.

5.3.6 Reflux/Gastritis

Antacids and other anti-ulcer medications such as histamine H₂-receptor antagonists may be used if clinically indicated. To avoid significantly altering gastric pH, when needed, these medications should be used 4 hours after study drug administration. Proton pump inhibitors such as omeprazole and lansoprazole, which have a potential for interaction with ARQ 197, should be avoided.

5.4 Duration of Therapy

In the absence of treatment delays due to adverse events, treatment may continue until one of the following criteria applies:

- Disease progression
- Intercurrent illness that prevents further administration of treatment

- Significant toxicity occurs despite 2 dose reductions as described in [Section 6](#) or no lower dose level exists
- Pregnancy
- Patient decides to withdraw from the study, or
- General or specific changes in the patient's condition render the patient unacceptable for further treatment in the judgment of the investigator.

5.5 Duration of Follow Up

Patients will be followed for 30 days after the last dose is administered or until one of the following occurs: patient enrolls on another protocol, patient receives standard of care, or death, whichever comes first. The follow-up will consist of a phone call between Days 27-30 after the last dose to evaluate adverse events that were ongoing and any new events that might be deemed related to the therapy. Toxicities felt to be possibly, probably, or definitely related to the study drugs that have not resolved or stabilized by Day 30 post-treatment will be followed until stabilization or resolution via biweekly phone calls.

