5.6 Criteria for Removal from Study

Patients will be removed from study for one of the following reasons: completed 30-day follow-up period or toxicities are unresolved but stabilized. The reason for study removal and the date the patient was removed must be documented in the medical record and communicated by fax to Central Registration per [Section 4](#).

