6.1.10 Management of Other Adverse Events

Adverse Event	Grade	Treatment Modification
Hemorrhage/ Bleeding	Grade 1	No interruption in treatment until hemoptysis. If hemoptysis, contact PI to determine if it is appropriate to continue pazopanib. Maintain current dose.
	Grade 2	For non-pulmonary bleeding, hold pazopanib unless resolved to \leq grade 1; reduce dose to next lower dose level, and continue treatment. For pulmonary bleeding, permanently discontinue pazopanib and remove subject from study. If grade 2 or greater hemorrhage/ bleeding recurs following dose reduction, stop pazopanib and remove subject from study.
	Grades 3 or 4	Discontinue treatment and withdraw subject from study.
Vascular/ Thrombosis	Grade 1	No interruption in treatment; maintain current dose.
	Grade 2, 3	Hold pazopanib until subject is receiving a stable dose of Low Molecular Weight Heparin (LMWH). Treatment may resume during the period of full-dose anticoagulation if all of the following criteria are met: 
 • The subject must have been treated with an anticoagulant at the desired level for at least one week. • The subject must not have had a grade 3 or 4 or significant grade 2 hemorrhagic event while on anticoagulant. Subject should be monitored as clinically indicated during anticoagulation treatment and after resuming study treatment. When treating with warfarin, international normalized ratio (INR) should be monitored within three to five days after any change in pazopanib dosing (e.g., re-initiating, escalating/de-escalating, or discontinuing pazopanib), and then at least weekly until the INR is stable. The dose of warfarin (or its derivatives) may need to be adjusted to maintain the desired level of anticoagulation.
	Grade 4 or pulmonary embolus	Discontinue treatment and remove subject from study.
Arterial Thrombosis/ ischemia	All grades	Discontinue pazopanib and remove subject from study.

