7.3 Expedited Adverse Event Reporting

7.3.1 Expedited AE reporting for this study must use CTEP-AERS (CTEP Adverse Event Reporting System), accessed via the CTEP Web site (<http://ctep.cancer.gov>). The reporting procedures to be followed are presented in the “CTEP, NCI Guidelines: Adverse Event Reporting Requirements” which can be downloaded from the CTEP Web site (<http://ctep.cancer.gov>). These requirements are briefly outlined in the table below ([Section 7.3.2](#)).

In the rare occurrence when Internet connectivity is lost, a 24-hour notification is to be made to CTEP by telephone at [REDACTED]. Once Internet connectivity is restored, the 24-hour notification phoned in **MUST** be entered electronically into CTEP-AERS by the original submitter at the site.

7.3.2 Phase 1 and Early Phase 2 Studies: Expedited Reporting Requirements for Adverse Events that Occur on Studies under an IND/IDE within 30 Days of the Last Administration of the Investigational Agent/Intervention ^{1,2}

FDA REPORTING REQUIREMENTS FOR SERIOUS ADVERSE EVENTS (21 CFR Part 312) NOTE: Investigators MUST immediately report to the sponsor (NCI) ANY Serious Adverse Events, whether or not they are considered related to the investigational agent(s)/intervention (21 CFR 312.64) An adverse event is considered serious if it results in ANY of the following outcomes:
 
 1) Death 2) A life-threatening adverse event 3) An adverse event that results in inpatient hospitalization or prolongation of existing hospitalization for ≥ 24 hours 4) A persistent or significant incapacity or substantial disruption of the ability to conduct normal life functions 5) A congenital anomaly/birth defect. 6) Important Medical Events (IME) that may not result in death, be life threatening, or require hospitalization may be considered serious when, based upon medical judgment, they may jeopardize the patient or subject and may require medical or surgical intervention to prevent one of the outcomes listed in this definition. (FDA, 21 CFR 312.32; ICH E2A and ICH E6). 		

ALL SERIOUS adverse events that meet the above criteria MUST be immediately reported to the NCI via CTEP-AERS within the timeframes detailed in the table below.
		
Hospitalization	Grade 1 and Grade 2 Timeframes	Grade 3-5 Timeframes

Resulting in Hospitalization ≥ 24 hrs	10 Calendar Days	24-Hour 5 Calendar Days
Not resulting in Hospitalization ≥ 24 hrs	Not required	

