7.3.4 NCI-IRB Expedited Reporting of Adverse Events, Unanticipated Problems, and Deaths

7.3.4.1 Definitions

Adverse Event

An adverse event is defined as any reaction, side effect, or untoward event that occurs during the course of the clinical trial associated with the use of a drug in humans, whether or not the event is considered related to the treatment or

clinically significant. For this study, AEs will include events reported by the patient, as well as clinically significant abnormal findings on physical examination or laboratory evaluation. A new illness, symptom, sign or clinically significant laboratory abnormality or worsening of a pre-existing condition or abnormality is considered an AE. All AEs must be recorded on the AE case report form.

All AEs, including clinically significant abnormal findings on laboratory evaluations, regardless of severity, will be followed until satisfactory resolution. AEs should be reported up to 30 days following the last dose of study drug. AEs that are considered treatment related, expected, continuing, but not resolvable by 30 days after treatment completion (e.g., alopecia) will not be followed after the 30-day period.

Suspected adverse reaction

Suspected adverse reaction means any adverse event for which there is a reasonable possibility that the drug caused the adverse event. For the purposes of IND safety reporting, ‘reasonable possibility’ means there is evidence to suggest a causal relationship between the drug and the adverse event. A suspected adverse reaction implies a lesser degree of certainty about causality than adverse reaction, which means any adverse event caused by a drug.

Unexpected adverse reaction

An adverse event or suspected adverse reaction is considered “unexpected” if it is not listed in the investigator brochure or is not listed at the specificity or severity that has been observed; or, if an investigator brochure is not required or available, is not consistent with the risk information described in the general investigational plan or elsewhere in the current application. “Unexpected” also refers to adverse events or suspected adverse reactions that are mentioned in the investigator brochure as occurring with a class of drugs or as anticipated from the pharmacological properties of the drug, but are not specifically mentioned as occurring with the particular drug under investigation.

Serious

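### Section 5.5 ends safety follow-up when other therapy starts, inside the protocol's own 30-day reporting window, and the rules that take patients off study for toxicity do not fit Section 5.6

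*Combined protocol and SAP*

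**What the plan says.** **Follow-up.** Section 5.5 opens with "Patients will be followed for 30 days after the last dose is administered" and continues "or until one of the following occurs: patient enrolls on another protocol, patient receives standard of care, or death, whichever comes first". The follow-up is one telephone call on Days 27-30, which asks about ongoing events and about new events that may be related. Related toxicities that are neither resolved nor stable at Day 30 "will be followed until stabilization or resolution via biweekly phone calls".

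**Reporting.** The heading of Section 7.3.2 covers "Adverse Events that Occur on Studies under an IND/IDE within 30 Days of the Last Administration of the Investigational Agent/Intervention", and serious events are reportable whether or not they are thought related. The Definitions text numbered 7.3.4.1, in the part on reporting to the IRB, says "AEs should be reported up to 30 days following the last dose of study drug". Neither section makes an exception for patients who start other therapy.

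**Leaving the study.** Section 5.6 states: "Patients will be removed from study for one of the following reasons: completed 30-day follow-up period or toxicities are unresolved but stabilized". Other sections take the patient off study at the event itself. For Grade 3 or 4 bleeding, for example, Section 6.1.10 says "Discontinue treatment and withdraw subject from study".

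**Calendars.** Both calendars (Sections 10.1 and 10.2) have an Off Treatment column that includes an adverse event evaluation. Neither gives it a day.

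**The concern.** Safety and tolerability is a primary objective, and Section 5.1.1 promises that all toxicities will be reported for everyone who receives any study drug. A reporting window works only if someone looks for events throughout it. For a patient who moves on early, Section 5.5 withdraws the one scheduled contact that would close the window, while Section 7 continues to treat the window as open.

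The days concerned are not empty ones. Because of pazopanib's long half-life, Section 5.3 asks for caution over drug interactions for 7 to 15 days after the last dose. A switch in the first two weeks can therefore fall while the protocol itself still regards the drug as relevant.

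The off-study wording adds a second uncertainty. Section 4 attaches an off-study form to going off study, so a site cannot tell whether a patient taken off for, say, arterial thrombosis stays in safety follow-up.

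**Working it through.** The plan states no figure here to reproduce, so the check is mainly a comparison of texts.

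**1. Follow-up against reporting window**

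| Question | Section 5.5 | Sections 7.3.2 and 7.3.4.1 (Definitions) |
|---|---|---|
| Length | 30 days, or earlier on new therapy or death | 30 days |
| Exception for new therapy | Yes | None |
| Events sought | Ongoing events, and new ones possibly related | All AEs; SAEs regardless of relation |

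A patient who switches on Day 26 or earlier is out of follow-up before the call is due. What remains is the undated Off Treatment evaluation. Section 5.6 also gives no removal reason that fits a patient whose follow-up ended early in this way.

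**2. Off-study wording against Section 5.6**

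The wording is applied to:
- repeat QTc of 500 msec or more (Section 5.3 and Table 6);
- nephrotic syndrome, and recurrent proteinuria when the dose can no longer be reduced (Table 5);
- Grade 2 pulmonary bleeding, recurrent bleeding of Grade 2 or more after dose reduction, and Grade 3-4 bleeding (Section 6.1.10);
- Grade 4 thrombosis or pulmonary embolus (Section 6.1.10);
- arterial thrombosis or ischemia of any grade (Section 6.1.10).

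None of these is among the two removal reasons in Section 5.6. The protocol has other language available: the opening of Section 6 stops therapy when toxicity outlasts the permitted delay and keeps the patient under follow-up for resolution.

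**3. Unresolved events at Day 30**

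The Definitions text first follows all AEs to satisfactory resolution. It then says that related, expected, continuing events that cannot resolve by Day 30 "will not be followed after the 30-day period", with alopecia as the example. Section 5.5 follows only related toxicities, and only until stable or resolved. For a stable, expected event such as alopecia the exception and Section 5.5 agree. Two cases still differ:
- an unrelated event ongoing at Day 30 is followed under the general rule in the Definitions but not under Section 5.5;
- a related, expected event judged not resolvable but not yet stable is followed under Section 5.5 but not under the exception.

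**4. Scale, under assumptions**

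Let d be the day on which other therapy starts. The share of the window outside follow-up is (30 − d)/30:
- d = 7: 23/30 = 77%
- d = 14: 16/30 = 53%
- d = 21: 9/30 = 30%

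If a share s of patients switches on Day 14, the person-time outside follow-up is s × 16/30: 13%, 27% and 40% for s = 25%, 50% and 75%.

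As an illustration, take s = 50%, d = 14, a true 30-day event rate of 10%, events spread evenly over the window, and no event found after the switch. The observable rate is 0.10 × (1 − 0.267) = 0.0733. The chance of seeing at least one event is then:
- 12 patients (expansion cohort): 1 − 0.90^12 = 72%, falling to 1 − 0.9267^12 = 60%
- 56 patients (accrual ceiling): 99.7%, falling to 98.6%

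The documents give neither d nor s. Because the illustration assumes that nothing is found after the switch, it is an upper bound on the loss for those inputs.

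**The case against.** The best defence is that Section 5.5 governs contact and does not cancel any duty to report. Sections 5.1.1, 7.3.2 and 7.4 require known events to be reported, and footnote 1 to Section 7.3.2 extends this to related serious events after Day 30. A reader might infer that events in the window are lost; the documents do not support that. The call is also not the only assessment after treatment, since the calendars plan an Off Treatment evaluation and Section 5.5 provides for biweekly calls on unresolved related toxicity. This stands, and it limits the point to planned ascertainment. It does not remove the gap, because the evaluation has no date and could fall on the day treatment stops.

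On the off-study wording, the defence is that it loosely means off treatment. Section 5.6 is the section that defines removal, and the opening of Section 6 shows that follow-up is intended. That is a plausible reading, and the text does not establish that sites would file the off-study form at the event. The two sets of passages still conflict as written.

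A reader might also infer that the truncation falls on the patients with the worst toxicity. The documents do not show this: combined transaminase and bilirubin elevation (Table 7), posterior leukoencephalopathy (Section 6.1.9) and Grade 4 hypertension (Table 3) stop pazopanib without taking the patient off study.

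Finally, a start of next therapy on Day 7 to 21 is not documented as typical. Some patients are eligible precisely because no standard option exists. That is correct, and the percentages are conditional on it.

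**Conclusion.** The point holds as an inconsistency in planned safety ascertainment. Sections 5.5 and 7 disagree on whether Days 0-30 are covered for a patient who starts other therapy, and the off-study wording in Section 5.3, Tables 5 and 6 and Section 6.1.10 disagrees with Section 5.6. The mismatch on unresolved events is real but narrow.

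For an affected patient, 30% to 77% of the window lies outside follow-up if other therapy starts between Day 21 and Day 7. That range is an assumption, and the share of patients affected is unknown.

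It would be tempting to conclude that the MTD is at risk. It is not on this ground: DLT is judged on cycle 1 (Section 5.1.1), and repeat QTc of 500 msec or more, Grade 3 or higher bleeding, Grade 2 or higher pulmonary bleeding, pulmonary embolism and arterial thrombosis are themselves DLT criteria in Section 5.2 when drug-related. What is exposed is the post-treatment part of the safety record. It should be corrected, since it bears on a primary objective and the remedy is small.

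**What to change.** - **Section 5.5:** continue AE and SAE collection, and make the Day 27-30 call, to Day 30 for every living, consenting patient whatever therapy follows. Record the start date of that therapy so that attribution can be judged.
- **Section 5.3, Tables 5 and 6, Section 6.1.10:** reconcile the off-study wording with Sections 5.5 and 5.6 so that it is clear that safety follow-up continues. No treatment-stopping rule needs to change.
- **Section 7.3.4.1 (Definitions):** align the sentences on unresolved events with Section 5.5, stating which events are followed after Day 30 and to what endpoint.

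The cost is amendment wording, one extra date field, and a call that is already planned. No sample size changes. The small downside is that some late events will be confounded by the next therapy; the recorded date lets them be identified and reported separately.

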5.6 Criteria for Removal from Study

Patients will be removed from study for one of the following reasons: completed 30-day follow-up period or toxicities are unresolved but stabilized. The reason for study removal and the date the patient was removed must be documented in the medical record and communicated by fax to Central Registration per [Section 4](#).

6 DOSING DELAYS/DOSE MODIFICATIONS

Toxicities (hematologic and non-hematologic; except any grade lymphopenia, anemia, or alopecia) should have resolved to \leq Grade 2 prior to starting the next cycle or receiving the next dose of pazopanib or ARQ 197 within a cycle. Study drugs should be held for hypokalemia or hyperkalemia \geq grade 2; hypocalcemia or hypercalcemia \geq grade 3; hypophosphatemia \geq grade 3; hypomagnesemia or hypermagnesemia \geq grade 3. These laboratory values should be corrected as soon as possible in a manner consistent with good medical judgment. Study drugs may be re-administered when hypokalemia or hyperkalemia is grade 1 or within institutional limits; hypocalcemia or hypercalcemia is \leq grade 2; hypophosphatemia is \leq grade 2; and hypomagnesemia or hypermagnesemia is \leq grade 2. Even though study drug administration is allowed at these lower grades, every effort should be made to correct the abnormal lab values to normal if possible. If the potassium level is grade 2 or greater and/or if the calcium, magnesium, and/or phosphate are grade 3 or higher, an EKG must be performed and appropriate action taken based on the results.

Treatment may be delayed for a maximum of 2 weeks for toxicities. In case toxicities do not resolve as stated, the patient will not receive further therapy on this protocol and will be followed for resolution of toxicities. Start of next cycle may be delayed for up to 1 week to accommodate scheduling conflicts. Dose modifications are intended for within-cycle and start-of-next-cycle changes. If administration of study drug is interrupted for any reason, it will not be made up, and

counting of the cycle days continues (i.e., if a patient stops pazopanib and ARQ 197 on day 15 and resumes 2 days later, they will be considered day 17).

A maximum of 2 dose reductions will be allowed before patient is taken off treatment. Patients who require a dose reduction will not have the dose re-escalated. Dose reductions may occur to a single compound independent of the other compound if toxicity necessitating a dose reduction is attributed to a single agent in the opinion of the study Principal Investigator. One dose level reduction due to pazopanib-associated toxicities such as hypertension means that pazopanib dose should be reduced to 400 mg if an original dose is 600 mg or to 600 mg if it is 800 mg. Similarly, one dose level reduction due to ARQ 197-associated toxicities means that ARQ 197 dose should be reduced to 120 mg bid if an original dose is 240 mg bid, or to 240 mg bid if it is 360 mg bid.

6.1 Dose Reduction

6.1.1 Doses will be modified for grade 3 or greater non-hematologic toxicity with the following clarifications:

- Doses will not be modified for electrolyte abnormalities, unless these are not correctable within 48 hours, or for alopecia.
- Dose of study drugs will not be reduced for nausea, vomiting, or diarrhea unless these are considered refractory as defined in [Section 5.3](#).
- Dose reductions may occur to a single compound, independent of the other compound. Doses of ARQ 197 will not be reduced for any grade hypertension or proteinuria.
- For uncontrolled hypertension (as defined in [Section 6.1.5](#)), only the dose of pazopanib will be reduced to the next lower dose level.
- For proteinuria, only the dose of pazopanib will be reduced to the next lower dose level ([Section 6.1.6](#)).

6.1.2 Grade 2 drug-related toxicity: No changes will be made to the dose of either study drug for Grade 2 toxicities, and therapy will not be interrupted, except as otherwise noted (e.g., hypokalemia or hyperkalemia as described above, Grade 2 hemorrhage or thrombosis as described in [Section 6.1.10](#)). However, for persistent symptomatic skin rash or hand foot syndrome limiting instrumental activities of daily living that do not improve to grade 1 or less within 2 weeks with optimal management, doses of both pazopanib and ARQ 197 will be held until toxicities have resolved to \leq Grade 1 prior to re-starting study treatment. Therapy will be re-initiated at the next lower dose level.

6.1.3 Grade 3 drug-related neutropenia and/or thrombocytopenia: Doses of both pazopanib and ARQ 197 will be held until toxicities have resolved to \leq Grade 2 prior to re-starting study treatment. Therapy will be re-initiated at the same dose level at the first occurrence of either event. In the case of second occurrence of

either event, therapy will be re-initiated at the next lower dose level. Therapy will not be interrupted or doses modified for any grade lymphopenia, anemia, or leucopenia in the absence of grade 3 or 4 neutropenia.

6.1.4 Grade 4 drug-related neutropenia ≥ 3 days and/or thrombocytopenia: Doses of both pazopanib and ARQ 197 will be held until toxicities have resolved to \leq Grade 2 prior to re-starting study treatment. Therapy will be re-initiated at the next lower dose level.

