5.2.1 Grade \geq 3 Non-Hematological Toxicity

Grade \geq 3 non-hematological toxicity felt to be related to study medications will be considered dose-limiting with the following clarifications:

- 5.2.1.1 Diarrhea Grade 3 will only be considered dose-limiting if it is refractory to treatment as outlined in [Section 5.3.2](#), Supportive Care Guidelines, and unable to be corrected to Grade 2 or less within 24 hours. Bloody or Grade 4 diarrhea will be dose-limiting.
- 5.2.1.2 Nausea and vomiting Grade 3 will only be considered dose-limiting if it is refractory to anti-emetic therapy and unable to be corrected to Grade 1 or less within 24 hours ([Section 5.3.1](#)).
- 5.2.1.3 Rise in creatinine to Grade 3, not corrected to Grade 1 or less within 48 hours with IV fluids will be considered dose-limiting. All Grade 4 rises in creatinine will be dose limiting.

5.2.1.4 Grade ≥ 3 metabolic toxicities unable to be corrected to Grade 2 or less within 48 hours (such as glucose changes, hypocalcemia or hypercalcemia, hypomagnesemia or hypermagnesemia, hyperuricemia, hypophosphatemia, and hyponatremia) will be considered dose limiting. For hypokalemia or hyperkalemia, grade ≥ 2 toxicities unable to be corrected to grade 1 or less within 48 hours will be considered dose limiting. Grade 4 metabolic toxicities that are symptomatic will be considered dose-limiting regardless of duration or ability to correct.

5.2.1.5 QTc prolongation to ≥ 500 msec on at least two separate EKGs (refer to [Section 5.3](#)) will be dose limiting.

5.2.1.6 AST/ALT > 8 X ULN or AST/ALT > 3 X ULN and concurrent bilirubin elevation > 2 X ULN will be dose limiting.

5.2.1.7 Grade ≥ 3 bleeding in any sites or grade ≥ 2 pulmonary bleeding will be dose limiting.

5.2.1.8 Grade 4 venous thrombosis, pulmonary embolism, or any grade of arterial thrombosis will be dose limiting.

5.2.2 Grade 4 thrombocytopenia.

5.2.3 Grade 4 neutropenia ≥ 3 days or febrile neutropenia.

5.2.4 Any degree of anemia, leucopenia in the absence of grade 4 neutropenia ≥ 3 days, or lymphopenia will not be considered dose limiting.

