7.2 Adverse Event Characteristics

- **CTCAE term (AE description) and grade:** The descriptions and grading scales found in the revised NCI Common Terminology Criteria for Adverse Events (CTCAE) version 4.0 will be utilized for AE reporting. All appropriate treatment areas should have access to a copy of the CTCAE version 4.0. A copy of the CTCAE version 4.0 can be downloaded from the CTEP web site http://ctep.cancer.gov/protocolDevelopment/electronic_applications/ctc.htm.

- **‘Expectedness’:** AEs can be ‘Unexpected’ or ‘Expected’ (see [Section 7.1](#) above) for expedited reporting purposes only. ‘Expected’ AEs (the ASAEL) are ***bold and italicized*** in the CAEPR ([Section 7.1](#)).
- **Attribution of the AE:**
 1. Definite – The AE *is clearly related* to the study treatment.
 2. Probable – The AE *is likely related* to the study treatment.
 3. Possible – The AE *may be related* to the study treatment.
 4. Unlikely – The AE *is doubtfully related* to the study treatment.
 5. Unrelated – The AE *is clearly NOT related* to the study treatment.

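### Section 6 never names febrile neutropenia, so one form of this DLT has no stated restart dose and another may restart at the same dose

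*Combined protocol and SAP*

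**What the plan says.** Sections 5.2.2 and 5.2.3 of the combined protocol and SAP define three hematologic DLTs. One is Grade 4 thrombocytopenia. The other two are in 5.2.3: Grade 4 neutropenia lasting at least "3 days or febrile neutropenia". Section 5.3.3 states: "Febrile neutropenia is a life-threatening complication requiring hospitalization". It also permits growth factors under ASCO "guidelines to allow re-treatment", so re-treatment after neutropenia is foreseen.

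Dose changes are set in Section 6:

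- **General text.** Toxicities must recover to Grade 2 or less before dosing resumes. "Treatment may be delayed for a maximum of 2 weeks for toxicities".
- **6.1.1.** "Doses will be modified for grade 3 or greater non-hematologic toxicity with the following clarifications".
- **6.1.3**, for Grade 3 drug-related neutropenia or thrombocytopenia: "Therapy will be re-initiated at the same dose level at the first occurrence of either event". A second occurrence restarts one level lower.
- **6.1.4.** The trigger is "Grade 4 drug-related neutropenia ≥ 3 days and/or thrombocytopenia", with restart one level lower.

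Section 5.1.2 takes a patient off treatment for a DLT during the single-agent pazopanib lead-in of the expansion cohort.

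**The concern.** The dose-reduction rule does not match the DLT definition it appears to follow. Section 6.1.4 carries over Grade 4 thrombocytopenia and the prolonged Grade 4 neutropenia from 5.2.2 and 5.2.3, but not febrile neutropenia. A patient could therefore resume the dose on which an event the protocol itself calls life-threatening occurred.

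The ordering looks unintended. A persistent Grade 2 rash or hand-foot syndrome that fails 2 weeks of management restarts one level lower (6.1.2). So does a second Grade 3 neutropenia without fever (6.1.3). Grade 2 non-pulmonary bleeding lowers pazopanib (6.1.10). No reason is given for treating febrile neutropenia more leniently.

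What is at stake is the individual patient's safety on re-treatment. DLTs are determined from cycle 1 only (5.1.1), whereas Section 6 governs dosing throughout, so the gap lasts as long as treatment does.

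**Working it through.** No arithmetic applies. The check sets the DLT triggers against the dose-modification triggers and asks, for each way febrile neutropenia can present, which rule fixes the restart dose.

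| Presentation | Rule that applies | Restart dose |
|---|---|---|
| Grade 4 count, 3 days or more | 6.1.4 | Next lower level |
| Grade 4 count, under 3 days | Neither 6.1.3 (Grade 3 only) nor 6.1.4 (3 days or more) | None stated |
| Grade 3 count, first event | 6.1.3, which has no exception for febrile neutropenia | Same level |
| Grade 3 count, second event | 6.1.3 | Next lower level |
| DLT in the expansion pazopanib lead-in | 5.1.2 | Off treatment |

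Rows 2 and 3 are the gap. The remaining provisions were then checked to see whether any of them fills it:

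- **6.1.1** is limited to non-hematologic toxicity. Febrile neutropenia sits with the hematologic DLTs in 5.2.3 and under blood and lymphatic disorders in both CAEPRs (7.1.1, 7.1.2). A separately graded Grade 3 or higher infection could trigger 6.1.1, but only if one is recorded.
- **The Section 6 hold** says when dosing may resume, not at what dose.
- **5.3.3** allows growth factors and gives no dose.
- **5.4** lets the investigator stop treatment. It is not a dose rule.
- **5.1.2** applies to the lead-in week only. ARQ 197 starts on day 8 in Cohort A, so it does not cover the combination.

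The Grade 3 rows rest on an assumption. The documents give no neutrophil threshold for febrile neutropenia. Section 7.2 says only that CTCAE "version 4.0 will be utilized for AE reporting" and does not reproduce the definition. If that definition excludes Grade 3 counts, those rows are empty and only row 2 remains. If febrile neutropenia is instead read as a term wholly separate from neutropenia, 6.1.3 and 6.1.4 do not reach it at all and the gap is wider.

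On frequency, Section 2.3.2 lists febrile neutropenia among serious events above 3% in the two single-agent ARQ 197 phase 1 studies, without attribution. Both CAEPRs put its relationship to the drug as undetermined. The three drug-related cases that led to discontinuation at 360 mg BID in the HCC study were neutropenia, not febrile neutropenia, and those patients were cirrhotic. None of this yields a count for rows 2 and 3.

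**The case against.** The best defence is that most of the ground is already covered. Prolonged Grade 4 cases are reduced, second Grade 3 events are reduced, and lead-in DLTs end treatment. Dosing cannot resume until toxicity is at Grade 2 or less, within 2 weeks, and the investigator may stop at any time. This stands, and it narrows the point: a reader might infer that no rule sets a restart dose for febrile neutropenia in any form, and 6.1.3 and 6.1.4 contradict that.

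It can also be said that row 2 is not specific to fever, because 6.1.3 and 6.1.4 set no restart dose for an afebrile Grade 4 count under 3 days either. That is correct. The difference is that the afebrile case is not a DLT under 5.2.3, whereas the febrile one is.

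Finally, for a Grade 3 count 6.1.3 gives an explicit instruction, so nothing is missing there. This is also true, but the instruction followed literally restarts a patient at the same dose after a DLT. None of the safeguards listed sets a lower dose for either open presentation.

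**Conclusion.** The point holds in a limited form. On the combination, febrile neutropenia with a Grade 4 count under 3 days has no stated restart dose. With a Grade 3 count, a first event restarts at the same dose under the literal text, provided CTCAE 4.0 allows febrile neutropenia at that count. The other presentations already lead to a reduction or to stopping.

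A reader might infer that the MTD is at risk. The documents do not support that: febrile neutropenia counts as a DLT under 5.2.3 whatever dose the patient later resumes, so escalation decisions are unchanged. Nor can the figure of above 3% in Section 2.3.2 be read as the share of patients affected here, since it carries no attribution and does not separate the two open presentations. Few patients are likely to be involved, and the number cannot be estimated from the documents. This is a cheap improvement to patient safety, not a flaw in the design.

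**What to change.** Change the 6.1.4 trigger to: *Drug-related Grade 4 neutropenia ≥ 3 days, febrile neutropenia, and/or Grade 4 thrombocytopenia*, keeping the existing hold to Grade 2 or less and restart at the next lower dose level. Add to 6.1.3: *except febrile neutropenia, see 6.1.4*.

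The exception should name febrile neutropenia, not fever. Fever is a listed pazopanib event (7.1.1), and a patient with Grade 3 neutropenia and a fever that does not meet the definition would otherwise fall outside both rules.

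The cost is a wording change in two subsections. The downside is that a few patients continue at a lower dose and use one of their two allowed reductions. The change does not set a restart dose for an afebrile Grade 4 count under 3 days, which the sponsor may wish to settle separately.
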